1 OVERVIEW AND INVESTIGATIONAL PLAN

This statistical analysis plan (SAP) provides a comprehensive and detailed description of statistical strategy and methodology to be used to analyze the data from sarilumab EFC15068 study in patients with giant cell arteritis (GCA).

Due to the ongoing pandemic of COVID-19 (the disease caused by the novel coronavirus), the operations of sarilumab (Kevzara®) clinical trial EFC15068 have been significantly disrupted in various countries and sites. Consequently, the screening/recruitment activities for this study have been suspended since 19th of March 2020. Due to the protracted recruitment timeline and internal portfolio reprioritization, in July 2020, Sanofi has decided not to re-open the screening/recruitment activities and to discontinue the study. This decision is not related to any safety issues arising from the administration of sarilumab.

A total of 83 patients (out of 360 planned patients) have been randomized in the study. While the number of randomized patients may not be adequate to demonstrate a statistically significant benefit, the data generated from the treated patients may contribute to the further understanding of IL-6 signaling blockade in this disease state.

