During the course of study, for patients in need of rescue therapy as per Investigator judgment, CS should be the agent of first choice. Patients may continue SC administration of sarilumab or matching placebo only if CS is used as the rescue therapy. If the patients remain symptomatic despite CS rescue therapy, then other treatment options including nonbiological immunosuppressive drugs may be used and the patient must be discontinued from the study treatment and considered a non-responder.

If the patient or Investigator decides to discontinue the administration of blinded sarilumab injections, then the patient will be asked to return to the site for study assessments as per protocol until end of study (EOS) evaluation, unless the patient cannot or does not wish to continue the assessments, in which case an early withdrawal visit and safety follow up should be performed. It is recommended that patients complete Visit 13, if possible.

Total duration of study participation for each patient is up to 82 weeks:

- Up to 6 weeks screening period.
- 52-week treatment period (sarilumab or placebo, double-blind phase).
- 24-week post treatment follow-up period.

The last patient last visit will occur when the last patient has completed the 24-week follow up period (EOS). The end of the clinical trial is defined as the last patient's last visit.

Study discontinuation plan

As mentioned in [Section 1](#), due to the protracted recruitment timeline and internal portfolio reprioritization, Sanofi has decided to terminate the EFC15068 study in July 2020. For patients who were already enrolled with ongoing treatment in the study, investigators were instructed to discontinue the study drugs and transition these patients into post-treatment follow-up period for safety assessments. The study discontinuation plan is as follows:

- All randomized patients should stop by 12 weeks from the date of announcement to the sites and should be scheduled for the end of study treatment visit at their earliest

convenience and no later than *October 13, 2020*, which would ensure sufficient time for patients to identify alternative therapy as needed.

- All patients will have a follow-up (EOS) visit that is 6 weeks after treatment cessation and no later than *November 24, 2020*.

Thus, the last patient last visit will occur when the last patient has completed the 6-week follow-up period (EOS). The end of the clinical trial is defined as the last patient's last visit.

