1.6 STATISTICAL MODIFICATIONS MADE IN THE STATISTICAL ANALYSIS PLAN

Due to the early termination of the study and study discontinuation plan, a large amount of data will not be able to be collected since many enrolled patients will not complete all planned study visits and study procedures for the assessments of efficacy, ADA, and biomarker endpoints. In addition, the number of randomized patients is 83 in 4 arms (out of 360 planned) at the time of the premature termination of the study. The changes from the statistical analysis plan outlined in the protocol are summarized below.

- The primary endpoint for the study is sustained remission at Week 52. Based on patients' enrollment dates and the study discontinuation plan, only about 36 patients (out of 83) had an opportunity to complete the 52-week treatment period. For the cohort of patients who

did not have an opportunity to complete the 52-week treatment period, it is not meaningful to define the endpoint of sustained remission at Week 52. Therefore, the analysis of primary endpoint will be limited to the cohort of patients who had an opportunity to complete the 52-week treatment period. Details can be found in [Section 2.1.3.1](#) and [Section 2.4.4.1](#).

- Based on patients' enrollment dates and the study discontinuation plan, all patients should have had the opportunity to be treated for at least 24 weeks, so an additional endpoint, sustained remission at Week 24, is added in the SAP. Details can be found in [Section 2.1.3.1](#).
- Due to the same reason as mentioned above, the secondary endpoints of cumulative GTI scores at Week 52 will be limited to the cohort of patients who had an opportunity to complete the 52-week treatment period. In addition, the cumulative GTI scores will also be assessed at Week 24. Details are provided in [Section 2.1.3.2](#).
- The missing data imputation strategy for defining the endpoints of sustained remission at W24 and W52, and cumulative GTI scores at W24 and W52 can be found in [Section 2.1.3.1](#) and [Section 2.1.3.2](#), respectively; the rest of efficacy analyses will be based on data as observed, no missing data will be imputed.

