- Constitutional syndrome, including but not limited to fever, malaise, unintentional weight loss, night sweat, asthenia, fatigue, loss of appetite.
- New or worsened extremity claudication, bruits and asymmetrical pulses.
- Other features judged by the Investigator to be consistent with a GCA or PMR flare.

The resolution of signs and symptoms of GCA is identified in eCRF “GCA Assessment” page with the question “Based upon the patient’s relevant medical history and the clinical assessment and responses provided above, does the patient have active GCA?” ticked as “No”. The resolution of signs and symptoms of GCA by Week 12 will be determined based on the last non-missing post-baseline GCA assessment measured up to Week 12.

Patients who took rescue CS due to active GCA prior to Week 12 or who permanently withdraw from the study treatment prior to Week 12 will be considered as not achieved disease remission by Week 12.

2. Absence of disease flare from Week 12 through Week 52.

Flare is defined as either 1) recurrence of signs and symptoms attributable to active GCA plus an increase in CS dose due to GCA, or 2) elevation of ESR attributable to active GCA plus an increase in CS dose due to GCA. Increase in CS dose is defined as:

- Any dose increase during the protocol defined steroid taper, or
- Reinitiation of prednisone therapy after the protocol defined taper has been completed.

Patients with disease flare are identified as those with the reason for treatment ticked “rescue therapy” in eCRF “Steroid Medication” page and to the question “If Rescue Therapy, please specify” ticked either “Active GCA” or “Elevated ESR Attributable to Active GCA”.

3. Normalization of CRP (to <10 mg/L, with an absence of successive elevations to ≥10 mg/L) from Week 12 through Week 52

The status of normalization of CRP from Week 12 through Week 52 will be determined based on the CRP values measured at Week 16, Week 20, Week 24, Week 32, Week 40 and Week 52. If there are two or more consecutive visits with CRP ≥10 mg/L, then it is categorized as no normalization of CRP. Intermittent missing CRP at Week 16, Week 20, Week 24, Week 32, Week 40 or Week 52 will be imputed using last value carried forward (LOCF) approach.

4. Successful adherence to the prednisone taper from Week 12 through Week 52

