Successful adherence to the prednisone taper from Week 12 through Week 24 is defined as patients did not take rescue therapy from Week 12 through Week 24 and may include the use of any excess prednisone (beyond the per protocol CS tapering regimen) with a cumulative dose of ≤100 mg (or equivalent), such as those employed to manage AE not related to GCA. The cumulative dose of excess prednisone use will be counted from baseline to Week 24.

In addition, patients who permanently withdraw from the study treatment prior to Week 24 will be considered as not achieved component 2, 3, or 4 for the primary endpoint.

Blinding of CRP and ESR assessment results

Investigators, including Efficacy Assessors, and patients will remain blinded to CRP and ESR results (except screening and baseline). Safety Assessors will also be blinded on post baseline CRP but will have access to ESR results.

ESR kits will be provided by the central laboratory while the test will be performed locally at site, results (the distance in millimeters (mm) that red blood cells has descended in 1 hour) will be blinded to Investigators including Efficacy Assessors and staff directly involved in efficacy assessment of study patients.

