Appendix C Summary of statistical analyses

Endpoint	Analysis		Statistical	Supportive	Subgroup	Other
	Population	Primary Analysis	Method	Analysis*	Analysis*	Analyses*
Primary Endpoint						
Patients who achieved sustained remission at Week 52	ITT	Proportion of patients achieving sustained remission at Week 52	CMH test stratified by baseline prednisone dose for combined groups, and descriptive analysis for non-combined groups.	1) Sensitivity analysis;2) Analysis excluding patients who prematurely withdraw from the study due to early termination of the study	No	No
Additional endpoint: Patients who achieved sustained remission at Week 24	ITT	Proportion of patients achieving sustained remission at Week 24	CMH test stratified by baseline prednisone dose for combined groups, and descriptive analysis for non-combined groups	Sensitivity analysis	No	No
Secondary Endpoints						
Patients who achieved of disease remission by Week 12	ITT	Proportion of patients who achieved of disease remission by Week 12	Descriptive	No	No	No
Patients who have absence of disease flare from Week 12 through Week 24 and Week 52	ITT	Proportion of patients who have absence of disease flare from Week 12 through Week 24 and Week 52	Descriptive	No	No	No
Patients who have normalization of CRP (decrease to <10 mg/L) with sustained normalization from Week	ITT	Proportion of patients who have normalization of CRP (decrease to <10 mg/L) with sustained normalization from Week 12 through Week 24 and Week 52	Descriptive	No	No	No

Endpoint	Analysis		Statistical	Supportive	Subgroup	Other
	Population	Primary Analysis	Method	Analysis*	Analysis*	Analyses*
12 through Week 24 and Week 52						
Patients who successfully adhere to the prednisone taper from Week 12 through Week 24 and Week 52	ITT	Proportion of patients who successfully adhere to the prednisone taper from Week 12 through Week 24 and Week 52	Descriptive	No	No	No
Total cumulative prednisone (or equivalent) dose	ITT	Total cumulative prednisone (or equivalent) dose over 52-week treatment period	Descriptive	No	No	No
Time to the first GCA flare after clinical remission up to Week 52	ITT	Time (from randomization) to the first GCA flare after clinical remission up to Week 52	Kaplan-Meier estimates and Cox proportional hazards model for combined groups, and descriptive analysis for non-combined groups.	No	No	No

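### Week 24 sustained remission: a patient taken off study drug by the sponsor's termination would count as a failure, and the supportive analysis for such stops is listed for Week 52 only

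*SAP*

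**What the plan says.** SAP section 2.1.3.1 defines sustained remission at Week 24 and closes with the rule that "patients who permanently withdraw from the study treatment prior to Week 24 will be considered as not achieved component 2, 3, or 4". The sentence ends by referring to the primary endpoint, but it stands under the Week 24 definition and I read it as applying there. Component 1 has a matching rule: patients who "permanently withdraw from the study treatment prior to Week 12 will be considered as not achieved disease remission by Week 12". Neither rule looks at the reason for stopping.

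The endpoint was added because "all patients should have had the opportunity to be treated for at least 24 weeks" (SAP 1.6; SAP 1.3 and 2.1.3.1 say the same). Section 2.4.4.1 analyses it in the ITT population of 83.

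On the calendar, SAP section 1 says "the screening/recruitment activities for this study have been suspended since 19th of March 2020" and dates the decision to discontinue to July 2020. Under the discontinuation plan in SAP 1.1, "investigators were instructed to discontinue the study drugs and transition these patients into post-treatment follow-up period for safety assessments", and "All randomized patients should stop by 12 weeks from the date of announcement to the sites". The end-of-treatment visit was to be as early as suited the patient, with 13 October 2020 as the outer limit.

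In Appendix C, the supportive-analysis column for Week 52 has two entries: a sensitivity analysis and "Analysis excluding patients who prematurely withdraw from the study due to early termination of the study". The Week 24 row has only the sensitivity analysis, which section 2.4.4.1 defines as removing CRP and ESR from the definition.

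**The concern.** Having the opportunity for 24 weeks is not the same as completing them. The opportunity holds for everyone if treatment ran towards the October limit. It need not hold for a late enrollee whose end-of-treatment visit was booked soon after the announcement. That patient, possibly in remission, would be a non-responder because of a portfolio decision that says nothing about the drug.

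The Week 52 Analysis set is also defined by opportunity at the outer date (SAP 2.3.1), yet Appendix C still adds an analysis that removes termination stops. The same reasoning was not carried to Week 24, the endpoint that uses all 83 patients and the only one for which Table 1 gives updated power. Since all p-values are nominal, what is at stake is mainly the estimated Week 24 rates and their difference.

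**Working it through.** **1. The plan's own figure.** Table 1 (SAP 1.3) has combined sarilumab 53%, n = 42, against combined placebo 17%, n = 41. For the 2-sided chi-square test with pooled variance under the null:

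Power = Φ[(|p1 − p2| − z·SE0)/SE1], with SE0 = √[p̄(1 − p̄)(1/n1 + 1/n2)] and SE1 = √[p1(1 − p1)/n1 + p2(1 − p2)/n2].

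- p̄ = (42 × 0.53 + 41 × 0.17)/83 = 0.352, SE0 = 0.105, SE1 = 0.097.
- Alpha 0.01: (0.36 − 2.576 × 0.105)/0.097 gives 82.3%. Alpha 0.05: (0.36 − 1.960 × 0.105)/0.097 gives 94.5%. Both match Table 1 (computed with unrounded standard errors).

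**2. Who is exposed.**

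- 13 October 2020 less 84 days is 21 July 2020. This announcement date is inferred; the SAP gives only July.
- Week 24 is Day 169, that is, randomisation plus 168 days. 21 July less 168 days is 4 February 2020, so a patient randomised later and stopped on 21 July is short of Week 24.
- Appendix H maps Days 155 to 196 to Week 24 for GCA assessments and CRP. If reaching Day 155 counts, the cut-off is 21 July less 154 days, or 18 February 2020. The SAP does not say which day applies.
- A patient randomised on 19 March 2020 reaches Day 169 on 3 September, 40 days before the limit. At the limit itself nobody randomised by that date is short.

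**3. How many.** The documents give no count. SAP 2.3.1 puts 36 patients before 16 October 2019, leaving 83 − 36 = 47. Assume these enrolled evenly over the 155 days to 19 March 2020, or 47/155 = 0.303 per day.

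- Everyone stays until Week 24: 0.
- End-of-treatment visits spread evenly over the 84 days (assumption): a patient s days short on 21 July stops too early with probability s/84, so the expected count is 0.303 × 44²/(2 × 84) = 3.5, about 4%. With the Day 155 reading, 0.303 × 30²/(2 × 84) = 1.6.
- Everyone stops on 21 July: 0.303 × 44 = 13, about 16%. With the Day 155 reading, 0.303 × 30 = 9.

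**4. Effect if stops are balanced and unrelated to outcome.** With a share f stopped and scored as failures, each rate becomes p(1 − f). If they are excluded, the rates stay and each n becomes n(1 − f).

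| Share stopped | Rates if scored as failures | Difference | Power, scored as failures (0.01/0.05) | Power, excluded (0.01/0.05) |
|---|---|---|---|---|
| 0 | 53.0% v 17.0% | 36 points | 82.3%/94.5% | same |
| 4% (3 to 4 patients) | 50.8% v 16.3% | 34.5 | 79%/93% | 80%/94% |
| 10% (about 8) | 47.7% v 15.3% | 32.4 | 74%/90% | 77%/92% |
| 16% (13) | 44.7% v 14.3% | 30 | 68%/87% | 73%/90% |

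Exclusion keeps the expected difference at 36 points in every row.

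**5. Effect if stops are unbalanced.** Four stops all in the sarilumab groups: 0.53 × 38/42 − 0.17 = 31.0 points. All four in the placebo groups: 0.53 − 0.17 × 37/41 = 37.7 points.

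**The case against.** A reader might infer that patients were in fact stopped before Week 24 and scored as failures, or that 13 of 83 is the expected number. The documents support neither. No section reports such a stop, and the SAP states, from enrolment dates, that all 83 could be treated for 24 weeks. The 13 needs even enrolment and every exposed patient stopping on an inferred date, whereas the plan allowed 12 weeks so that patients could find another therapy. A reader might also expect exclusion to restore the lost power. It restores the expected difference but only part of the power: 68% to 73% at 0.01 and 87% to 90% at 0.05 in the worst case.

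Three further points have weight. All analyses are descriptive and p-values nominal (SAP 1.6 and 2.4.4.3), so no formal decision turns on the power. Balanced stops shrink the difference and so do not flatter sarilumab. The SAP also already tabulates discontinuations before Week 24 with reasons (section 2.2), and time to first flare censors remitters without a flare at end of treatment.

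These points limit the severity but do not close the gap. The disposition table shows how many stopped without correcting the Week 24 rates. Time to flare is a different estimate. With 83 patients, balance between arms is not assured.

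**Conclusion.** The point holds as an omission. The Week 24 rule makes no allowance for sponsor-ordered stops, and no analysis in the SAP handles them at Week 24, although one is listed for Week 52. Its size is unknown and may be zero. Under the stated assumptions the expected loss is about 1.5 points of a 36-point difference in the middle case and about 6 points at worst, with bias possible in either direction if the arms differ. The range rests on even enrolment of the 47 later patients, enrolment ending on 19 March 2020, an announcement on 21 July 2020, and stopping unrelated to outcome. It is smaller if Day 155 counts as Week 24. Severity is low. The ITT analysis remains sound as the main Week 24 result and needs only this companion.

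**What to change.** Make four additions to the SAP, leaving the ITT analysis as the main Week 24 result.

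1. In the Week 24 row of Appendix C and in section 2.4.4.1, add the supportive analysis already listed for Week 52, excluding patients whose study treatment was stopped before Week 24 because of the sponsor's termination. Word it by stop of study treatment, as the failure rule is, since the Week 52 entry speaks of leaving the study. Section 2.4.4.1 does not describe the Week 52 entry either, so one paragraph can cover both.
2. Run it also restricted by randomisation date, with the cut-off set from the actual announcement date. Excluding by reason alone keeps early failures among late enrollees while dropping those still in remission; a date rule treats both alike. Its small cost is that it also drops late enrollees who completed Week 24.
3. State whether the Week 24 withdrawal rule runs to Day 169 or to the Day 155 start of the window.
4. Report termination stops before Week 24 by arm, from the disposition data already planned.

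The cost is two extra runs of an existing analysis on data already collected. If the count is zero, one sentence in the report closes the matter.

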2.1.3.2 Secondary efficacy endpoint(s)

The following efficacy variables will be assessed:

- Components of sustained remission composite measure at Week 52 and Week 24
- Total cumulative corticosteroid (including prednisone) dose over during the treatment period
- Time to first GCA flare during the treatment period

- GTI Cumulative worsening score (CWS) and Aggregate improvement score (AIS) at Week 52 and Week 24.

Below are descriptions of these variables. Details related to imputation of GTI scores are described in [Section 2.5.2](#).

Components of sustained remission composite measure at Week 52

1. Proportion of patients who achieved disease remission by Week 12.
2. Proportion of patients who have no disease flare from Week 12 through Week 52.
3. Proportion of patients who have normalization of CRP (to <10 mg/L, with an absence of successive elevations to ≥ 10 mg/L) from Week 12 through Week 52.
4. Proportion of patients who successfully adhere to the prednisone taper from Week 12 through Week 52.

Components of sustained remission composite measure at Week 24

1. Proportion of patients who achieved disease remission by Week 12.
2. Proportion of patients who have no disease flare from Week 12 through Week 24.
3. Proportion of patients who have normalization of CRP (to <10 mg/L, with an absence of successive elevations to ≥ 10 mg/L) from Week 12 through Week 24.
4. Proportion of patients who successfully adhere to the prednisone taper from Week 12 through Week 24.

Total cumulative corticosteroid (including prednisone) dose during the treatment period

The total cumulative corticosteroid includes prednisone taper regimen per protocol, use of prednisone (an excess of ≤ 100 mg of prednisone during the study treatment period such as those employed to manage AE not related to GCA is permissible for meeting the definition of maintenance of sustained remission) and rescue corticosteroids dose prescribed for rescue therapy over the treatment period for GCA disease only.

Time to first GCA flare during the treatment period

The duration (in days) from randomization to first GCA flare after clinical remission and up to 52 weeks. Patients who never achieve remission will be censored at randomization day; and those who achieved clinical remission and never flared will be censored at the end of treatment assessment date up to Week 52.

The definition of GCA flare is provide in [Section 2.1.3.1](#) primary efficacy endpoint.

Clinical remission is defined as resolution of signs and symptoms and normalization of CRP (<10 mg/L). Intermittent missing CRP at visit will be imputed using last value carried forward (LOCF) approach. If missing signs and symptoms, then clinical remission is not achieved.

Glucocorticoid toxicity index (GTI) scores and components

The GTI is intended to capture glucocorticoid (GC)-related morbidity and GC-sparing ability of other therapies (2).

The GTI is composed of two components, the Composite GTI and the Specific List (Table 4). The Composite GTI consists of nine domains (body mass index (BMI), glucose tolerance, blood pressure, Hyperlipidemia, Bone Health (BMD), steroid myopathy, Skin steroid-related Toxicity, Neuropsychiatric - steroid related symptoms and infection) on common steroid-related adverse events anticipated to occur in $\geq 5\%$ of patients treated in a clinical trial involving glucocorticoids. The Specific List consists of 23 items (11 domains) that are mainly less common but serious adverse effects, serving as a complementary tool to the Composite GTI to ensure that all important elements of glucocorticoid toxicity were captured.

The domains of the Composite GTI and the specific list of the GTI will be assessed at baseline, Week 12, Week 24, Week 40 and Week 52, except for bone density (BMD) which will be assessed at Baseline and Week 52 only.

Please note, due to early termination of the study, most patients will not have BMD assessed at Week 52. In addition, for patients who withdraw from the study prior to Week 24, the BMD will not be measured at the EOT visit as no substantial changes are expected within 6 months of treatment. As a result, missing BMD score will be imputed as 'no change'. The BMD measured at the end of treatment (EOT) visit will be included in the definition of cumulative GTI scores (i.e., CWS and AIS as defined below) at Week 52 regardless when the EOT visit is occurred. The BMD domain score will be set to 'no change' in the calculation of the cumulative GTI scores at Week 24.

Scoring of the Glucocorticoid Toxicity Index (GTI)

Domain-specific score for each patient at a visit is defined as the weight assigned based on the change in severity level as described for each domain in Table 4.

Composite GTI score for each patient at a visit is the sum of 9 domain-specific scores at each visit.

Cumulative GTI score is the sum of composite GTI score across visits. Two cumulative GTI scores, CWS and AIS, will be defined.

- **Cumulative worsening score (CWS)**

CWS is designed to assess cumulative GC toxicity, regardless of whether the toxicity has lasting effects or is transient. New toxicities that occur are added, but toxicities that appear to resolve on follow-up are not removed. Thus, the CWS serves as a lasting record of GC toxicity observed and can only increase or remain the same over time.

CWS will be lower in the treatment arm compared to the placebo arm at the end of trial, if the treatment is effective at decreasing GC toxicity over time.

- **Aggregate improvement score (AIS)**

Patients are anticipated to have some GC toxicity at baseline, the AIS would be important in establishing that the new therapy is effective at diminishing any baseline GC toxicity over time. With the AIS, toxicities can be removed if improvement occurs, and added if worsening occurs.

AIS decrease over time means that the treatment is effective in decreasing GC toxicity level, compared to placebo which may show fluctuation of CIS over time. Negative score reflects that toxicities present at baseline (or occurring during the trial) resolved over the treatment period.

The steps to calculate the CWS and AIS at Week 24 and Week 52 are described below.

Step 1: Calculate domain-specific worsening score (for computing CWS in Step 2) and improvement score (for computing AIS in Step 2) at each visit.

For Domains without sub-items (Body Weight, Glucose Metabolism, Blood Pressure, Lipid Metabolism, Bone Health and Steroid Myopathy),

- a) For worsening score, only consider positive domain-specific score at each visit. For domain with a negative domain-specific score, the worsening score will be 0.
- b) For improvement score, all domain-specific scores (could be positive or negative) at each visit will be considered.

The Skin and Neuropsychiatric domains both have sub-items. For the Skin domain, these are Acneiform Rash, Easy Bruising, Hirsutism, Atrophy/Striae, and Erosions/tears/ulcerations. For the Neuropsychiatric domain, these are Insomnia, Depression, Mania, and Cognitive Impairment.

- a) For worsening score, only the item with the highest weight is scored for any GTI interval (typically three months) with the CWS. As an example, if neither insomnia nor depression were present at the baseline visit but there is now mild Insomnia and moderate depression present at follow-up, then only the moderate depression is scored (+63 points).
- b) For improvement score, improvement as well as worsening can be recorded. Because it is conceivable that one item might improve while another worsens, the item of greatest improvement (highest absolute weight) and the item of greatest worsening (highest weight) are recorded for given GTI interval.

For Infection Domain, the worsening score and improvement score handle the scoring of infections differently, because the CWS and AIS reflect reciprocal measures of GC toxicity.

- a) For worsening score, the most severe infection in every GTI interval is scored.
- b) For improvement score, only the most severe infection occurring over the course of the entire trial is scored.

Step 2: Calculate composite worsening score and improvement score at each visit by summing the 9 domain-specific score.

- a) For composite worsening score, sum the 9 domain-specific worsening scores.

- b) For composite improvement score, sum the 9 domain-specific improvement scores.

Step 3: Calculate cumulative GTI scores by summing composite scores across visits.

- a) For CWS at Week 24, summing composite GTI worsening score at Week 12 and Week 24.
- b) For CWS at Week 52, summing composite GTI worsening score at Week 12, Week 24, Week 40, and Week 52.
- c) For AIS at Week 24, summing composite GTI improvement score at Week 12 and Week 24.
- d) For AIS at Week 52, summing composite GTI improvement score at Week 12, Week 24, Week 40, and Week 52.

Table 4 – The Glucocorticoid Toxicity Index

Composite GTI	Item weight	Specific List¹
1.BMI		
Decrease by \geq 5 BMI units	-36	Major increase in BMI
Decrease by >2 but <5 BMI units	-21	
No significant change (\pm 2 BMI units)	0	
Increase of >2 to <5 BMI units	21	
Increase of 5 or more BMI units	36	
2.Glucose tolerance		
Improvement in HbA1c AND decrease in medication	-44	Diabetic retinopathy
Improvement in HbA1c OR decrease in medication	-32	Diabetic nephropathy
No significant change	0	Diabetic neuropathy
Increase in HbA1c OR increase in medication	32	
Increase in HbA1c AND increase in medication	44	
3.Blood pressure		
Improvement in BP AND decrease in medication	-44	Hypertensive emergency
Improvement in BP OR decrease in medication	-19	Posterior reversible encephalopathy syndrome
No significant change	0	
Increase in BP OR increase in medication	19	
Increase in BP AND increase in medication	44	
4.Hyperlipidemia		
Decrease in LDL AND decrease in medication	-30	
Decrease in LDL OR decrease in medication	-10	
No significant change	0	
Increase in LDL OR increase in medication	10	
Increase in LDL AND increase in medication	30	
5.Bone Health (BMD)		
Increase in BMD (gain of more than 3%)	-29	Major decrease in bone density
No significant change in BMD (\pm 3%)	0	Insufficiency fracture

Composite GTI	Item weight	Specific List¹
Decrease in BMD (loss of more than 3%)	29	
6.Steroid myopathy		
Moderate weakness to none	-63	Severe steroid myopathy
Moderate to Mild weakness	-54	
Mild weakness to none	-9	
No significant change	0	
None to Mild weakness (without functional limitation)	9	
Mild to Moderate weakness	54	
None to Moderate weakness (with functional limitation)	63	
7.Skin steroid-related Toxicity		
Decrease in Skin Toxicity - Moderate to None	-26	Severe skin toxicity
Decrease in Skin Toxicity - Moderate to Mild	-18	
Decrease in Skin Toxicity - Mild to None	-8	
No significant change	0	
Increase in Skin Toxicity - None to Mild	8	
Increase in Skin Toxicity - Mild to Moderate	18	
Increase in Skin Toxicity - None to Moderate	26	
8.Neuropsychiatric - steroid related symptoms		
Decrease in NP Toxicity - Moderate to None	-74	Psychosis
Decrease in NP Toxicity - Moderate to Mild	-63	GC-induced violence
Decrease in NP Toxicity - Mild to None	-11	Other severe neuropsychiatric symptoms
No significant change	0	
Increase in NP Toxicity - None to Mild	11	
Increase in NP Toxicity - Mild to Moderate	63	
Increase in NP Toxicity - None to Moderate	74	
9.Infection		
No infection	0	Grade IV infection
Oral or vaginal candidiasis or non-complicated zoster (<Grade3)	19	Grade V infection
Grade 3, 4, or 5 infection	93	

¹ Maximum weight is given for specific list events in Blood pressure, Steroid myopathy, Skin toxicity, Neuropsychiatric and Infection domains at each visit. For the rest of domains, specific list events will not affect the corresponding domain specific score.

